6.6.2 Other endpoints and safety endpoints

With respect to the SLEDAI, no missing item(s) will be imputed. If one item comprising the sub-score is missing, the sub-score will be set to missing. Other sub-scores will be derived and analysed. If one item is missing, the total score will be set to missing.

Missing or incomplete AE dates are imputed according to BI standards (see “Handling of missing and incomplete AE dates”). [\(1\)](#)

All other endpoints will be analysed without imputing for any missing data.

6.7 BASELINE, TIME WINDOWS AND CALCULATED VISITS

Since patients are randomized at the start of 1293.10 and on the same treatment in 1293.13, the baseline of trial 1293.10 will be used as baseline for all assessments of change from baseline if not specified otherwise. The baseline is defined as the latest time point on or before the date of the first randomised treatment administration (the date of the first dose is acceptable because the first dose of medication is to be taken in clinic on the day of randomisation AFTER all baseline assessments have been made) in 1293.10. If there is no measurement for a particular variable on or before the date of first randomised treatment administration, then no baseline will be derived for that variable.

Visit 1 of trial 1293.13 was to be performed on the same day as the 1293.10 end of treatment (EOT) visit. All assessments performed at the 1293.10 EOT visit were used as baseline for this 1293.13 and were not repeated.

The following visit labels will be used in 1293.13 tables & graphics. As specified in the CTP, EOT refers to the End of Treatment visit. EOS is the End of Study visit. FU is Follow Up.

For discontinued patients who do not continue participation in the trial:

EOT = ‘EOT’

For completed patients:

Week 52=‘Week 52/ EOT’

Follow-up visit at Week 56=‘FU’

End of study visit at Week 64=‘EOS’

Patient who discontinued treatment before week 40 & continued in trial:

Proprietary confidential information © 2021 Boehringer Ingelheim International GmbH or one or more of its affiliated companies

EOT='EOT'

Visit 4='Visit 4/FU'

Visit 6='Visit 6/FU'

Visit 8='Visit 8/FU'

EOS='EOS/FU'

Patient who discontinued treatment after week 40 & continued in trial:

EOT='EOT'

Visit 8='Visit 8/FU'

Visit EOS='EOS/FU' This is the 'week 52' visit

Visit EOS='EOS + 12w/FU' This is the 'week 52' plus 12 weeks visit

Visit labels containing 'Visit' or 'FU' occurred after the EOT visit; patient was not on drug for these visits.

7. PLANNED ANALYSIS

For End-Of-Text (EoT) tables, the set of summary statistics is: N / Mean / SD / Min / Median / Max.

For tables that are provided for endpoints with some extreme data, median, quartiles and percentiles should be preferred to mean, standard deviation, minimum and maximum.

Tabulations of frequencies for categorical data will include all possible categories and will display the number of observations in a category as well as the percentage (%) relative to the respective treatment group (unless otherwise specified, all patients in the respective patient set whether they have non-missing values or not). Percentages will be rounded to one decimal place. The category missing will be displayed only if there are missing values.

All calculated statistics will be presented to one more decimal place than the original measurement accuracy of the variable being summarised.

All p-values will be displayed to four decimal places (or “<0.0001” if appropriate).

7.1 DEMOGRAPHIC AND OTHER BASELINE CHARACTERISTICS

Only descriptive statistics are planned for this section of the report. The display will include the following variables: gender, ethnicity, race, age, time since diagnosis (months) at the time of entry to 1293.10, height, weight, smoking status, alcohol status, LN class, FACIT-F total score, anti-double stranded DexoxyriboNucleic Acid (anti-dsDNA), Complement Component C3 (C3) and Complement Component C4 (C4) counts at baseline, eGFR at baseline, UP/UC from the spot urine at baseline, UP from the 24h collection at baseline and UP/UC from the 24h collection at baseline, modified activity and chronicity index scores. Baseline is the baseline of 1293.10.

7.2 CONCOMITANT DISEASES AND MEDICATION

Concomitant diseases and medications will be summarized. Frequency counts are planned.

Concomitant diseases will be coded using the current version of MedDRA coding system.

Medications will be coded using the WHO Drug dictionary (WHO-DD). The coding version number will be displayed as a footnote in the respective output.

In addition to the standard display showing all concomitant medications, a separate display will be provided to characterize usage of ACEi (Angiotensin-converting enzyme inhibitors) and ARBs (Angiotensin receptor blockers) by treatment group as these therapies may impact renal response. A separate display will be provided to characterize usage of antimalarial therapies by treatment group as usage of antimalarial therapies may impact occurrence of renal flares.

For individual patients who experience renal flares, their usage of antimalarial therapies may be explored.

Proprietary confidential information © 2021 Boehringer Ingelheim International GmbH or one or more of its affiliated companies

For the non-standard displays, it is of interest to capture the number of patients who use these meds at:

- Baseline
- On-treatment
Including any changes such as: therapies newly started, dose increases, therapies stopped and dose decreases
- At week 52 (when patient is evaluated for the primary endpoint)

Concomitant diagnoses and medications will be listed by patient. Subjects without any concomitant diagnosis or therapy should be marked with a “No” in the respective column.

7.3 TREATMENT COMPLIANCE

Only descriptive statistics are planned for this section of the report.

7.4 PRIMARY ENDPOINT

7.4.1 Primary analysis of the primary endpoint

Primary analyses of the primary endpoint will be performed using the ITT patient set.

Proportion of patients with CRR at Week 52 without renal flare (derived using UP and derived using UP/UC from the 24h urine collections) will be analysed using a logistic regression model. Factors in the model will include treatment and the covariates: race (Asian/non-Asian) and proteinuria at screening $<3\text{g/day}$ or $\geq 3\text{g/day}$ (respectively $\text{Uprot/Ucreat}<3$ or $\text{Uprot/Ucreat}\geq 3$) in 1293.10.

Pairwise comparisons of the *modelled* proportion of patients at each dose level who are CRRs without renal flare will be compared to placebo. In keeping with the exploratory nature of the trial, p-values will be interpreted in a nominal fashion (no adjustment for multiplicity will be performed).

Pairwise comparisons of the *observed* proportion of patients at each dose level who are CRRs without renal flare will be compared to placebo. Confidence intervals will be calculated using the Newcombe method. P-values from Barnard tests of association will be displayed.

Pairwise comparisons of *stratified observed* proportions of patients at each dose level who are CRRs without renal flare will be compared to placebo. Confidence intervals will be calculated using the Cochran-Mantel-Haenszel (CMH) method. A single p-value from a CMH test of general association will be displayed.

For 1293.10 it was decided that for the pairwise comparisons, an alpha level of < 0.20 (two-sided) would be the cut-off for declaring statistical significance. This will be adopted for 1293.13. However, it is important when interpreting the p-values (and numerical comparisons) to keep the trial design with its inherent biases in mind. This is an extension trial with the requirement to entry that patients responded to treatment in 1293.10 and have

Proprietary confidential information © 2021 Boehringer Ingelheim International GmbH or one or more of its affiliated companies

the desire to continue participation in a clinical trial. Treatment assignments were not randomized and numbers of patients per treatment group are not balanced.

The partial unblinding of treatment codes for the risk-benefit discussions between investigators and patients is not expected to have a meaningful impact on this primary endpoint derived from laboratory measurements.

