3. DESCRIPTION OF DESIGN AND TRIAL POPULATION

3.1 OVERALL TRIAL DESIGN AND PLAN

This is a phase II, double-blind, parallel-design, dose-ranging, placebo-controlled, exploratory maintenance trial. The trial is designed to evaluate the long term efficacy and safety of different doses of BI 655064 in patients with LN; and to study the effect of steroid tapering and steroid withdrawal during 52 weeks of maintenance treatment.

[figure not shown]
This trial is had been planned to include up to two groups of patients:

- Group 1 are roll-over patients that have achieved either a CRR or a PRR or proteinuria ≤ 1.0 g/d (or UP/UC ≤ 1) at the end of 1293.10.
- Group 2 was not started as the predefined criteria to start the group was not met (cf. Ch 1.2)

In addition to receiving either BI 655064 or placebo, all entered patients will continue to receive SOC treatment, and steroids tapering will be performed. Refer to Figure 3.1:1 below and section 4.2.1 for more information. This trial consists, and of a 52-week treatment period; followed by safety assessments at FUp and EOS visits (Flow Charts). The primary analysis will be performed in all treated patients to assess the proportion of patients with CRR after 52 weeks of treatment and without any renal flares.

Study Design: Patients from 1293.10 (Group 1)

Patients will continue to receive the same treatment arm as previously assigned in 1293.10

* For patients with CRR or proteinuria $< 0.8\text{g/d}$: steroids tapering should start immediately at Visit 1 and steroids should be stopped at Week 12.

** For patients with proteinuria $\geq 0.8\text{g/d}$: steroids should be tapered down to $\leq 7.5\text{mg/d}$ at Week 26 and then to $\leq 5\text{mg/d}$ at Week 52.

Figure 3.1:1 Outline of trial design – Group 1

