3.2 DISCUSSION OF TRIAL DESIGN, INCLUDING THE CHOICE OF CONTROL GROUP

The design of this trial together with the 1293.10 (dose-finding, efficacy and safety of BI 655064 in patients with active LN) is intended to facilitate the selection of appropriate dose regimens for further confirmation in the Phase III trials.

The treatment duration of 52 weeks was selected based on feedback from external experts and recommendation in the currently available EMA guideline for at least one year maintenance treatment following induction therapy for LN ([R15-3716](#)).

Group 1 are patients that have achieved a renal response or proteinuria ≤ 1.0 g/d (or UP/UC ≤ 1) at the end of 1293.10; it is therefore justifiable for these patients to continue receiving the same treatment arm as previously assigned in 1293.10 during the maintenance phase. This is to ensure both patients and investigators remain blinded in order to allow comparisons of efficacy and safety of different doses in a population that appears to be able to safely receive the same dose as in the 1293.10 induction study. The patients will continue to receive one injection per week at Visit 1 of either BI 655064 (120mg/180mg/) or Placebo for up to 52 weeks (12 months). Patients on 240mg receive one injection of 120mg every week.

After topline data from trial 1293.10 became available, an independent DMC reviewed these topline data and unblinded safety and efficacy data of Group 1 patients in trial 1293-0013. The DMC recommended to continue trial 1293-0013 as planned.

The Boehringer Ingelheim Benefit Risk Committee (BRC) assessed the benefit-risk of BI 655064 for patients in Group 1 of trial 1293 13 (responders from trial 1293.10). The BRC took into consideration the recommendation to continue the trial given by the DMC and concluded that the benefit-risk for patients in Group 1 of trial 12930013 is unchanged for responders but decided that investigators should be informed about topline data and should receive treatment information for those patients remaining in Group 1 of trials 1293-0013. The investigator and the patient should thoroughly discuss treatment options and the patient's continuing participation in 1293-0013. Following this decision, a total of 29 patients (20 on treatment, 9 in follow-up) were unblinded.

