4.1.3 Method of assigning patients to treatment groups

Group 1 patients will continue to receive the same treatment allocation as previously assigned in the 1293.10 trial (i.e., either 120mg or 180mg or 240mg or Placebo) at Visit 1.

The assignment will occur in a blinded fashion via Interactive Response Technology (IRT). Details regarding the use of IRT are described in the site IRT user manual available in the ISF.

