7.7 DETERMINATION OF SAMPLE SIZE

It is estimated that 60 responders from 1293.10 will be prepared to roll-over into 1293-0013.

There is no power calculation for this.

8. INFORMED CONSENT, TRIAL RECORDS, DATA PROTECTION, PUBLICATION POLICY, AND ADMINISTRATIVE STRUCTURE

The trial will be carried out in compliance with the protocol, the ethical principles laid down in the Declaration of Helsinki, in accordance with the ICH Harmonized Tripartite Guideline for Good Clinical Practice (GCP), relevant BI Standard Operating Procedures (SOPs), the EU regulation 536/2014, the Japanese GCP regulations (Ministry of Health and Welfare Ordinance No. 28, March 27, 1997) and other relevant regulations.

Standard medical care (prophylactic, diagnostic and therapeutic procedures) remains the responsibility of the treating physician of the patient.

The investigator will inform the sponsor immediately of any urgent safety measures taken to protect the trial patients against any immediate hazard, as well as of any serious breaches of the protocol or of ICH GCP.

The Boehringer Ingelheim transparency and publication policy can be found on the following web page: trials.boehringer-ingelheim.com. The rights of the investigator and of the sponsor with regard to publication of the results of this trial are described in the investigator contract. As a rule, no trial results should be published prior to finalisation of the Clinical Trial Report.

The certificate of insurance cover is made available to the investigator and the patients and is stored in the ISF.

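### The stratified dose-versus-placebo comparisons in SAP 7.4.1 carry one overall CMH p-value that, read as written, tests none of them; a dose-trend statistic would be a cheap exploratory addition

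*SAP*

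**What the plan says.** SAP 7.4.1 plans three sets of comparisons for the primary endpoint, complete renal response (CRR) at week 52 without renal flare:

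- A logistic model with treatment, race and screening proteinuria, from which each dose's modelled proportion is compared with placebo.
- Unstratified observed proportions, each dose against placebo, with Newcombe intervals and Barnard p-values (plural).
- A stratified version: "Pairwise comparisons of *stratified observed* proportions of patients at each dose level who are CRRs without renal flare will be compared to placebo". Intervals come from the CMH method, and then: "A single p-value from a CMH test of general association will be displayed".

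The same section adopts a two-sided 0.20 cut-off for declaring significance in the pairwise comparisons, without multiplicity adjustment. SAP 7.4.2 adds pairwise comparisons by race and by proteinuria, and a pooled 180+240 mg comparison with placebo. SAP 7.5.2 applies the primary endpoint's methods to the binary secondary endpoints.

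The arms are "i.e., either 120mg or 180mg or 240mg or Placebo" (Protocol 4.1.3). Protocol 3.1 describes the design: "This is a phase II, double-blind, parallel-design, dose-ranging, placebo-controlled, exploratory maintenance trial". Protocol 3.2 says the trial, together with 1293.10, "is intended to facilitate the selection of appropriate dose regimens for further confirmation in the Phase III trials". On size, Protocol 7.7 says "It is estimated that 60 responders from 1293.10 will be prepared to roll-over into 1293-0013" and "There is no power calculation for this". SAP 7.4.1 adds that "numbers of patients per treatment group are not balanced".

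**The concern.** The stratified display sets three questions (does 120, 180 or 240 mg differ from placebo?) and gives an interval for each. The one p-value beside them answers a fourth question: do the four arms differ in any way at all? A difference between two active doses is enough to make it small. A reader applying the 0.20 cut-off could therefore credit a dose that does not differ from placebo, or overlook one that does.

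A second, lesser point is that the doses are ordered, yet no visible analysis uses the order. The logistic model lists treatment as a factor, with no dose score or ordered contrast. The 180+240 mg pool leaves out 120 mg and cannot separate 180 from 240 mg.

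**Working it through.** The documents give no power figure, response rates or per-arm numbers, so there is nothing to reproduce. Inputs from the documents: four arms, about 60 patients, unequal arms, two-sided 0.20. Assumed: 15 per arm (20/10/10/20 as a check) and all response rates. SAP 7.4.1 does not name the strata for this analysis, so the examples are unstratified.

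**1. Degrees of freedom.** General association with four arms and a binary outcome has (4 − 1) × (2 − 1) = 3 df. The SAP does not state this; it follows from one p-value covering four arms.

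**2. Overall test below 0.20 with no dose different from placebo.** Responders out of 15 on placebo/120/180/240 mg: 8/5/11/8.

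- Pooled rate p = 32/60 = 0.533. Expected responders per arm = 8. Variance term 15p(1 − p) = 3.733.
- Overall: Σ(r − 8)²/3.733 = (0 + 9 + 9 + 0)/3.733 = 4.821. The CMH form multiplies by 59/60, giving 4.741. On 3 df, **p = 0.192**.
- 120 mg v placebo: 30 × (8×10 − 7×5)²/(15×15×13×17) = 60750/49725 = 1.222, **p = 0.27**.
- 180 mg v placebo: 30 × (8×4 − 7×11)²/(15×15×19×11) = 60750/47025 = 1.292, **p = 0.26**.
- 240 mg v placebo: 8 against 8, **p = 1.00**.
- With the CMH factor 29/30 the first two become 0.277 and 0.264. Barnard gives 0.32, 0.30 and 1.00.

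The overall result comes from 120 mg against 180 mg (5 v 11): 30 × (5×4 − 10×11)²/(15×15×16×14) = 243000/50400 = 4.82 on 1 df, p = 0.028.

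**3. The opposite error.** Responders 6/7/8/10.

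- Overall p = 0.513. The 1-df CMH-form p for 240 mg against placebo is 0.150 (Barnard 0.23).
- Trend, scores 0/120/180/240: T = Σ score × (r − 7.75) = 0 − 90 + 45 + 540 = 495. Scores have mean 135 and squared deviations summing to 18225 + 225 + 2025 + 11025 = 31500. With p = 31/60, the variance is 0.24972 × 15 × 31500 = 117994. T²/V × 59/60 = 2.042, p = 0.153.

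**4. What a trend test would add.** Two-sided 0.20, 15 per arm, rates linear in dose (35/47.5/53.75/60%), by simulation:

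| Test | Power |
|---|---|
| Trend, 1 df | 57% |
| Overall, 3 df | 46% |
| 240 mg v placebo (chi-square) | 55% |
| 180+240 mg pool v placebo (chi-square) | 55% |

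Noncentral chi-square power agrees in direction. For linear 40 to 65%, trend has 56.5% and overall 45.1% (63.7% and 51.2% with 20/10/10/20).

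**5. When the ordering reverses.** At 80% power and alpha 0.20, the 3-df test needs noncentrality 6.53 and the 1-df test 4.50. Trend therefore wins only if it captures more than about 4.50/6.53 = 0.69 of the between-arm signal. With equal arms, that share is the squared correlation between the dose scores and the response pattern:

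| Pattern (placebo/120/180/240) | Share | Trend v overall power at 0.20 |
|---|---|---|
| Linear 40 to 65% | 1.00 | 56.5% v 45.1% |
| Plateau 40/60/60/60% | 135²/(31500×0.75) = 0.77 | 46.8% v 42.3% |
| 120 mg inactive 40/40/60/60% | 150²/(31500×1) = 0.71 | 51.6% v 48.7% |
| Only 240 mg works | 105²/(31500×0.75) = 0.47 | overall ahead |
| 120 mg below placebo 40/25/60/60% | 32.25²/(31500×0.086875) = 0.38 | 55.5% v 72.6% |

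The first three patterns are above 0.69 and favour trend; the last two are below it and favour the overall test. Allocation matters: with 20/10/10/20 the share when only 240 mg works is 2200²/(606000×13.33) = 0.60, so trend's disadvantage shrinks.

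**The case against.** The strongest reply is that the plan already answers the pairwise questions elsewhere. The logistic model uses all four arms, adjusts for race and screening proteinuria, and compares each dose with placebo; Barnard p-values do the same without adjustment. That stands, and it confines the defect to one of three displays. A reader might infer that the plan has no valid p-value for a dose against placebo. The documents do not support that.

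Second, the 3 df are inferred. The sentence sits in a paragraph about pairwise comparisons and could mean one CMH test per pair. In a stratified 2×2 layout the general-association and correlation statistics coincide on 1 df. That reading is possible, but the word "single" and the plural used for Barnard in the preceding paragraph point the other way. Under either reading the sentence needs an edit.

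Third, a reader might conclude that omitting a trend test is an error in a trial whose purpose is dose selection. That goes too far. Protocol 3.2 assigns dose selection to this trial together with 1293.10. The main objectives in Protocol 2.1.1 concern doses versus placebo, and Protocol 7.3.1 carries over the pairwise methods of 1293.10. In the linear case the trend test beats the planned pairwise and pooled comparisons by only about 2 points. SAP 7.4.2 also reports unexpected findings in the 120 mg group, the kind of pattern that may favour the overall test. Entry required a response or low proteinuria in 1293.10, so a slope across these arms is not a randomised dose-response estimate. All of this stands.

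Finally, SAP 6.4 and 7.6 and Protocol 7.3.3 are not in the available text, so the absence of an ordered-dose analysis can be stated only for what is visible.

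**Conclusion.** The p-value point holds, within limits. As written, the one p-value in the stratified display does not test the comparisons beside it, and it can disagree with them in either direction at the SAP's own cut-off. The numerical examples rest on an assumed 15 per arm and chosen counts. They show that the disagreement can occur, not how often it will.

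The trend test is an optional improvement, not a correction. The claim that the overall test has less power for a dose response is true only for responses close enough to monotone. It fails if 120 mg is worse than placebo and, with equal arms, if only 240 mg works.

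Severity is minor to moderate: the analyses are exploratory, p-values are nominal, no power is claimed, and other dose-placebo tests are planned.

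**What to change.** In SAP 7.4.1, and wherever 7.5.2 reuses the method (including confirmed CRR):

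1. Show a 1-df stratified CMH p-value for each dose against placebo beside its CMH interval, and name the strata.
2. If the overall p-value is kept, label it as a four-arm test of any difference, and state that the pairwise 0.20 cut-off does not apply to it.
3. Optionally add, beside the pairwise results and not in their place, the stratified CMH trend statistic with scores 0/120/180/240 and a logistic dose slope with its interval. Label both exploratory. Note that they assume a roughly monotone response, that the arms were selected by response in 1293.10, and that they are unbalanced.

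The cost is a few lines of code on existing data. The drawbacks are more nominal p-values per endpoint and a trend result that can miss a non-monotone response.

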7.4.2 Sensitivity analysis, subgroup analysis, exploratory analysis of the primary endpoint

Sensitivity analyses:

Pairwise comparisons of the *observed* proportions of patients at each dose level to placebo who are CRRs without renal flare will be stratified *by race* (Asian vs. non-Asian) as a sensitivity analysis. Confidence intervals will be calculated using the Newcombe method. P-values from Barnard tests of association will be displayed. This same analysis will be performed for *observed* placebo-adjusted proportions of patients at each dose stratified *by proteinuria at screening in 1293.10* (UP/UC < 3 vs. UP/UC ≥ 3) as per the lab results. These analyses will be performed for CRR derived using UP determined from the 24h collections, UP/UC determined from the 24h collections and confirmed CRR.

Exploratory analyses:

The *observed* proportion of patients who are CRRs without renal flare in the 180 mg and 240 mg dose groups combined will be compared to placebo, displaying the same confidence intervals and p-values as noted above. This is an exploratory analysis, based on unexpected findings/imbbalances observed in the 120 mg group at the time of the interim analysis of 1293.10. Analyses will be performed for CRR derived using UP determined from the 24h collections and confirmed CRR. These analyses were added via this version of the TSAP.

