7.3.2 Secondary endpoint analyses

Secondary endpoints ([Section 2.1.3](#)) will be analysed in the same way as the primary endpoint. For the endpoint of time to first renal flare, a Kaplan Meier curve will be presented. Further details will be provided in the TSAP.

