7.5.1.1 Primary analysis of the key secondary endpoint

7.5.1.2 Sensitivity analysis, subgroup analysis, exploratory analysis of the key secondary endpoint

7.5.2 (Other) Secondary endpoints

Analysis of all secondary endpoints will be performed using the ITT population.

Proprietary confidential information © 2021 Boehringer Ingelheim International GmbH or one or more of its affiliated companies

For the secondary endpoints listed below, the pairwise comparison of observed proportion of patients at each dose level will be compared to placebo using the same methods outlined for the primary endpoint.

- Proportion of patients with confirmed CRR without renal flare
- Proportion of patients with proteinuria <0.8g/d and without any renal flares
- Proportion of patients with CRR and sustained steroid reduction to ≤ 5 mg/d without renal flare
- Proportion of patients experiencing at least one renal flare
- Proportion of patients with partial renal response (PRR) without renal flare

At the time this TSAP was prepared, 8 renal flares were known to have occurred. The secondary endpoint, time to renal flare, will be displayed using a Kaplan Meier curve across all treatment groups to explore the timing of renal flares with color-coding, symbols or an embedded table to indicate the treatment group in which they occurred.

For the secondary endpoint, change from baseline in the SLEDAI, descriptive statistics will be provided.

Due to the perceived importance of the secondary endpoint, confirmed CRR, the logistic analyses described for the primary analysis will be performed and the sensitivity analyses by race and by proteinuria at screening in 1293.10 will be performed.

The analysis of proportion of patients with CRR having sustained steroid reduction ≤ 5 mg from week 26 will be repeated for confirmed CRR. The proportion of patients with confirmed CRR or confirmed PRR will be analysed. The analysis of proportion of patients with CRR who were steroid free from week 26 will be repeated for confirmed CRR. The exploratory analysis combining 180mg and 240mg BI 655064 versus placebo will be repeated for confirmed CRR.

At the time this TSAP was prepared, the expectation is that confirmed CRR will be more sensitive than the primary endpoint for detecting treatment effects within subgroups. For this reason, the secondary endpoint, confirmed CRR, will be used for exploring treatment effects within subgroups.

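### The pooled 180+240 mg comparison with placebo is planned only on unadjusted observed proportions, while the single-dose comparisons of the same endpoints also get a covariate-adjusted model

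*SAP*

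**What the plan says.** SAP 7.4.1 gives the primary endpoint three kinds of comparison with placebo, each with its own label:

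- *Modelled* proportions come from a logistic regression: "Factors in the model will include treatment and the covariates: race (Asian/non-Asian) and proteinuria at screening" (below 3 g/day, or 3 g/day and above, in 1293.10).
- *Observed* proportions get Newcombe intervals, and "P-values from Barnard tests of association will be displayed".
- For *stratified observed* proportions, "Confidence intervals will be calculated using the Cochran-Mantel-Haenszel (CMH) method", with one CMH p-value. The strata are not named.

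SAP 7.4.2 then plans the pooled comparison on the observed proportion, "in the 180 mg and 240 mg dose groups combined will be compared to placebo, displaying the same confidence intervals and p-values as noted above". It covers CRR from the 24-hour urine protein and confirmed CRR, and SAP 7.5.2 repeats it for confirmed CRR. The race and proteinuria sensitivity analyses in 7.4.2 are defined for each dose level, not for the pool.

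For the binary secondary endpoints, SAP 7.5.2 says that each "pairwise comparison of observed proportion of patients at each dose level will be compared to placebo using the same methods outlined for the primary endpoint". It assigns the logistic analyses to confirmed CRR alone. Protocol 7.3.2 says secondary endpoints "will be analysed in the same way as the primary endpoint" and leaves details to the SAP.

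On design, SAP 7.4.1 warns of inherent biases because entry required a response in 1293.10, and adds: "Treatment assignments were not randomized and numbers of patients per treatment group are not balanced".

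**The concern.** Patients were randomised at the start of 1293.10, but only responders who chose to continue came into this trial. That selects on an outcome measured after randomisation. If active drug and placebo bring different kinds of patients to response, the arms that roll over can differ in prognosis even though the original arms did not.

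A crude difference in proportions mixes any treatment effect with such differences. The sponsor already uses race and screening proteinuria as covariates for the single-dose comparisons of both endpoints. The pooled contrast uses more treated patients than any single-dose contrast, yet no covariate-adjusted version of it is specified. A reader who sees the pooled and modelled single-dose results disagree could not tell whether pooling or the missing covariates was the cause.

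**Working it through.** The documents give no figure to reproduce. Protocol 7.7 estimates about 60 patients and states that there is no power calculation; arm sizes, response rates and covariate distributions are not given. The two-sided 0.20 cut-off (SAP 7.4.1), the total of about 60 and the 8 known flares (SAP 7.5.2) come from the documents. Everything else below is assumed. Equal arms would give 60/4 = 15 each, hence 30 pooled against 15 placebo; the SAP says the arms are in fact unequal.

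**1. What is specified**

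| Comparison | Logistic, two covariates | Observed (Newcombe/Barnard) | CMH-stratified |
|---|---|---|---|
| Single dose, CRR without flare | yes | yes | yes |
| Single dose, confirmed CRR | yes | yes | by cross-reference to the primary methods |
| Pooled 180+240 mg, both endpoints | no | yes | not on the plain reading |
| Other binary secondary endpoints | not named | yes | unclear |

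**2. Bias in a crude difference.** With no treatment effect within strata, bias = (difference in response between strata) × (difference between arms in the share in the high stratum). Assume CRR of 70% with screening proteinuria below 3 and 40% at 3 or above, and 25% of pooled patients against 45% of placebo patients in the high stratum:

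(0.70 − 0.40) × (0.45 − 0.25) = 0.06, or 6 points.

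**3. Effect on the nominal 0.20 error.** This was simulated with no treatment effect within strata: 30 v 15 patients, one binary covariate, response differing by 10 to 30 points between strata, and 200,000 runs per scenario. The crude test was a pooled-variance z test standing in for Barnard.

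| Imbalance | Bias (points) | Crude error | CMH error |
|---|---|---|---|
| 0 points | 0 | 0.19–0.20 | 0.19–0.20 |
| 13 points | 1–4 | 0.20–0.21 | 0.20 |
| 23 points | 2–7 | 0.21–0.24 | 0.20 |
| 37 points | 4–11 | 0.22–0.30 | 0.20–0.21 |

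Harm therefore needs a covariate that is both prognostic and clearly imbalanced.

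**4. Power.** Assume 50% v 75% response.

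- SE = √(0.75×0.25/30 + 0.50×0.50/15) = 0.151, and 0.25/0.151 = 1.65. Against the critical value 1.28, unadjusted power is about 65%.
- For the covariate in step 2 with 35% of patients in the high stratum, overall response is 0.65×0.70 + 0.35×0.40 = 0.595. Its correlation with response is 0.30×√(0.35×0.65)/√(0.595×0.405) = 0.29.
- Multiplying the variance by 1 − 0.29² gives SE 0.145, ratio 1.73 and power of about 67%. The gain is 2 to 3 points.

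**5. Limits on adjustment.** For renal flare, a model with three treatment and two covariate terms would have 8/5 = 1.6 events per parameter. For CMH, two races by two proteinuria levels by four arms gives 16 cells, or 60/16 = 3.75 patients per cell on average.

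**The case against.** The strongest reply is that these are exploratory analyses with nominal p-values, that SAP 7.4.1 already tells the reader to keep the selection bias in mind, and that race and screening proteinuria may not capture that bias. SAP 7.5.2 itself names time since diagnosis as prognostic, and that factor is not in the model. All of this is fair. It limits what adjustment can achieve, but it does not explain why the pooled contrast should lack the adjustment that its component doses receive.

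A second reply is that the reference to intervals and p-values noted above could reach back to the CMH method. That is possible, but the section uses the plain *observed* label and the nearest methods above it are Newcombe and Barnard. On either reading no logistic contrast is named.

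A reader might infer four stronger points, which the documents do not support:

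- *That the other binary secondary endpoints ignore the covariates.* SAP 7.5.2 points to the methods of the primary endpoint, and these include the CMH comparison, itself a comparison of observed proportions.
- *That the SAP departs from the protocol.* Protocol 7.3.1 names no covariates or logistic model. It speaks of numerical comparison of response rates and of the 1293.10 pairwise methods, and leaves details to the SAP.
- *That the SAP admits covariate imbalance.* The sentence "Treatment assignments were not randomized and numbers of patients per treatment group are not balanced" concerns patient numbers, and unequal arm sizes alone do not confound.
- *That chance imbalance makes the crude test invalid.* With 30 v 15 patients and 35% in the high stratum, the SD of the imbalance is √(0.35×0.65×(1/30 + 1/15)) = 0.151, so 15 points or more arises about 32% of the time. That also happens in a randomised trial and is not bias.

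**Conclusion.** The concern holds for the pooled 180+240 mg comparison, for both CRR without flare and confirmed CRR: no covariate-adjusted estimate is specified, although the single-dose comparisons of both endpoints have one. The reason to add it is selection on response at roll-over, not unequal arm sizes. For the other binary secondary endpoints the finding is only that the wording leaves the CMH comparison and its strata open.

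The size is conditional. Under the assumed inputs the crude pooled difference could carry 1 to 11 points that are not treatment, and the nominal 0.20 error could reach about 0.30 in the most extreme case tried. With no imbalance it stays near 0.20. The documents give neither the prognostic strength of the covariates nor their imbalance. Adjustment reduces but need not remove selection bias, and a power gain of 2 to 3 points is not a reason in itself. The change is worth making mainly because it costs so little.

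**What to change.** - In SAP 7.4.2, and where 7.5.2 repeats the pooled analysis for confirmed CRR, add the 180+240 mg v placebo contrast from the 7.4.1 logistic model with the same two covariates. Show the CMH-stratified risk difference and interval beside it, and keep the Newcombe and Barnard results.
- In SAP 7.4.1, name the CMH strata (race and 1293.10 screening proteinuria, if those are meant).
- In SAP 7.5.2, state that the methods carried over from the primary endpoint include the CMH-stratified comparison. Fit no regression for renal flare.

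The cost is SAP wording and a few output columns from analyses already planned for the primary endpoint, with no new data. The downside is sparseness: with about 60 patients in four arms, a stratum that lacks one of the compared arms contributes nothing to the CMH estimate, so the number of informative strata and patients should be reported with it.
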